5.2.5.6. Hospitalization events

If a subject is admitted to the hospital, the participant will remain in the study and follow the procedures outlined in the visit schedule. Hospitalization is defined as inpatient admission.

The date of hospitalization events will be recorded in the CRF and includes:

- Hospitalization
- Emergency room visit: only for dosed subjects that last 24 hours or longer will be included
- ICU admittance
- Extended care facility (ECF) admittance: ECF events will only be documented for subjects dosed in the trial who experience adverse events (AEs) and require additional medical support in the ECF, such as respiratory therapy to address the AEs. The requirement for additional medical support in the ECF is considered comparable to hospitalization as a discretion by the investigator. This means ECF events occurring before trial enrollment will not be documented. Additionally, enrolled subjects without experiencing AEs move to the ECF after enrollment will not be considered hospitalized and do not need to be entered into the EDC.
- Discharge

5.2.5.7. Clinical Status and Medications/Procedures of Special Interest

The subject's clinical status and concurrent medications/procedures of special interest will be recorded in the CRF, including the level of consciousness, limitation on activities due to CAP, and requirements for the following:

- Ongoing hospital medical care
- Supplemental oxygen
- Non-invasive ventilation or a high flow oxygen device
- Mechanical ventilation
- ECMO
- Additional organ support (e.g., pressors, renal replacement)

5.2.5.8. Respiratory Support

Once enrolled in the study, subjects may be managed with high-flow nasal cannula, noninvasive positive pressure ventilation or any other form respiratory support as needed per investigator discretion

5.2.5.9. Pregnancy test

A urine or blood pregnancy test should be performed in women of childbearing potential at screening visit and Day 7. Subject should carry out efficient birth control throughout the study period.

5.2.5.10. Treatment Emergent Adverse Events (TEAEs)

The treatment emergent adverse events will be collected from the start of treatment to the end of study.

The detail of adverse event will be referred to **Section 6 Adverse Events**.

6. ADVERSE EVENTS

The treatment emergent adverse event (TEAE) and serious adverse event (SAE) will be recorded from the start of treatment until the end of study.

Any pre-treatment medical events will be recorded as medical history.

6.1. Adverse Event (AE)

An adverse event (AE) can therefore be any unfavorable and unintended sign (including an abnormal laboratory finding, for example), symptom, or disease temporally associated with the use of a medicinal product, whether or not considered related to the study medication. (Definition per International Conference on Harmonization [ICH]). A medical occurrence fulfills the definition of SAE in section 6.2 is also an AE.

Except for SAEs, Adverse Events are NOT:

- Clinical events related to expected progression of COVID-19 or influenza.
- Medical or surgical procedures (e.g., surgery, endoscopy, tooth extraction, transfusion). However, the condition that leads to the procedure is an AE.
- Situations where an untoward medical occurrence has not occurred (e.g., hospitalization for elective surgery, social and/or convenience admissions).

6.1.1. Treatment Emergent Adverse Event (TEAE)

A treatment-emergent adverse event (TEAE) is defined as any unfavorable and unintended disease or its sign (including an abnormal laboratory value) in a subject who received the study drug, irrespective of the causal relationship with the study drug.

6.2. Serious Adverse Event (SAE)

The definition of a Serious Adverse Event (SAE) is any untoward (negative with respect to the subject's pre-operative condition) medical occurrence that:

- Results in death,
- Is life threatening (immediately as it occurred, not had it become worse at some time in the future),
- Requires hospitalization (or a prolongation of hospitalization in already hospitalized patients),
- Results in a persistent or significant disability or incapacity, or

- Is a congenital anomaly or birth defect.

There are medical events that may not require inpatient hospitalization, be immediately life threatening, or result in death but may jeopardize the subject or may require intervention to prevent one of the other outcomes listed before. Medical and scientific judgments should be exercised in deciding whether an event should be reported as a “Serious Adverse Event.”

Nevertheless, the following events will NOT be reported as a SAE:

- Hospitalization due to social reasons in absence of an adverse event
- Hospitalization due to surgery or procedure planned before entry into the study (must be documented in the CRF)
- Hospitalization for elective treatment of a pre-existing condition that did not worsen from baseline

6.3. Severity of Adverse Events

The investigator should use clinical judgment in assessing the severity of events not directly experienced by the subject (e.g., laboratory abnormalities).

The grade refers to the severity of the AE using CTCAE Version 5.0 (published on November 27, 2017). The CTCAE displays Grade 1 to 5 with unique clinical descriptions of severity for each AE as shown in below:

Table 6-1 Grading scales of AEs

Grades of AEs	Description
Grade 1	Mild; asymptomatic or mild symptoms; clinical or diagnostic observations only; intervention not indicated.
Grade 2	Moderate; minimal, local or noninvasive intervention indicated; limiting age-appropriate instrumental ADL*
Grade 3	Severe or medically significant but not immediately life-threatening; hospitalization or prolongation of hospitalization indicated; disabling, limiting self-care ADL**
Grade 4	Life-threatening consequences; urgent intervention indicated.
Grade 5	Death related to AE.

* Activities of daily living (ADL) refer to preparing meals, shopping for groceries or clothes, using the telephone, managing money, etc.

** Self-care ADL refer to bathing, dressing and undressing, feeding self, using the toilet, taking medication, and not bedridden.

6.4. Associated with the Use of the Medication

An adverse event is considered associated with the use of the drug if the attribution is certain, probably/likely, possible, or unlikely by the definitions listed as follows. The causal relationship between AEs and study drug modified from WHO-UMC system for standardized case causality assessment.

Table 6-2 Causality categories between AEs and study drug

Causality term	Assessment criteria
Certain	
• Event or laboratory test abnormality, with plausible time relationship to drug intake• Cannot be explained by disease or other drugs• Response to withdrawal plausible (pharmacologically, pathologically)• Event definitive pharmacologically or phenomenologically (i.e., an objective and specific medical disorder or a recognized pharmacological phenomenon)• Rechallenge satisfactory, if necessary
Probable / Likely	
• Event or laboratory test abnormality, with reasonable time relationship to drug intake• Unlikely to be attributed to disease or other drugs• Response to withdrawal clinically reasonable• Rechallenge not required
Possible	
• Event or laboratory test abnormality, with reasonable time relationship to drug intake• Could also be explained by disease or other drugs• Information on drug withdrawal may be lacking or unclear
Unlikely	
• Event or laboratory test abnormality, with a time to drug intake that makes a relationship improbable (but not impossible)• Disease or other drugs provide plausible explanations
Unrelated	
• Occurred before dosing• Due wholly to factors other than study treatment

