3.4. Discontinuation of Study Intervention

Discontinuation of study product CX-4945/placebo does not mean discontinuation from the study, and the remaining study procedures will be completed as designated by this protocol. If a clinically significant finding is identified following the initiation of study treatment, the Investigator (or designee) will determine if any change in subject management is necessary. However, a subject should be discontinued from study product CX-4945/placebo in any of the following circumstances:

- A suspected Grade 3 or higher treatment-related AE (according to Common Terminology Criteria for Adverse Events (CTCAE) version 5.0)
- Any treatment-related SAE
- A subject receives baricitinib
- A subject receives warfarin
- The subject is pregnant

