7.8.1. Treatment-emergent Adverse Events (TEAEs)

This analysis applies to all treatment-emergent adverse events occurring during the study, recorded in AE eCRF. AEs occurring during the study will be coded using the most recent version of Medical Dictionary for Regulatory Activities (MedDRA). The adverse events will then be grouped by MedDRA preferred terms into frequency tables according to system organ class. All reported adverse events, as well as adverse events judged by the investigator as at least possibly related to IP, will be summarized according to system organ class and preferred term within system organ class. When an adverse event occurs more than once for a subject, the maximal severity to the IP will be counted.

An overview of TEAEs will be presented with number and percentage. Separate summaries will be produced for the following categories, such as TEAEs, SAEs, Treatment-Related TEAEs, TEAEs resulting in discontinuation of study treatment and TEAEs leading to death will be presented. All coding terms will be included in the subject data listing.

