## **2.2 RANDOMIZATION AND BLINDING**

The study treatment will be randomly assigned to subjects. The randomized sequence of study treatments will be generated by a qualified biostatistician. The randomization schedule will be kept and maintained by the designated personnel before the study begins and until the database lock. The biostatistician prepares the schedule with a 1:1 randomization ratio (CX-4945: Placebo) by stratified randomization with study domains and study sites strata. Also, block permutation is used for generating randomization schedule.

This is a double-blind study. Neither the subject nor the investigators, clinic administrators, or sponsor staff who involve in the treatment or clinical evaluation of the subjects will be aware of the treatment received either at the time of randomization or later, throughout the conduct of the trial. Assigned unblinded team may include study site staff, CRO's personnel and/or Senhwa Biosciences, Inc's personnel. Other personnels involved in the study (the investigator and the clinical monitor) will be blinded until the database lock.

The treatment codes will not be prematurely broken unless an emergency situation, when the appropriate management of the subject necessitated acknowledgement of the treatment allocation, occurred. In the event of a medical emergency, if possible, the medical monitor should be contacted first to discuss the need for unblinding. For unblinding a subject, the treatment code blind can be obtained by the investigator, by accessing the EDC system.

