**3.2.5 SAFETY ANALYSES**

**Treatment-emergent Adverse Events (TEAEs)**

**Statistical Analysis Plan**  
CX-4945 for Community-Acquired Pneumonia

---

AEs occurring during the study will be coded using the most recent version of Medical Dictionary for Regulatory Activities (MedDRA). The adverse events will then be grouped by MedDRA preferred terms into frequency tables according to system organ class. All reported adverse events, as well as adverse events judged by the investigator as at least possibly related to IP, will be summarized according to system organ class and preferred term within system organ class. When an adverse event occurs more than once for a subject, the maximal severity to the IP will be counted.

An overview of TEAEs will be presented with number and percentage. Separate summaries will be produced for the following categories, such as TEAEs, SAEs, Treatment-Related TEAEs, TEAEs resulting in discontinuation of study treatment and TEAEs leading to death will be presented. All coding terms will be included in the subject data listing.

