#### **3.4.1 STATISTICAL METHODS CHANGE**

Due to early termination of the study, only 44 subjects were randomized. For both the primary and secondary endpoints, the number of events observed prior to unblinding was insufficient to support reliable estimation using logistic regression. Therefore, Logistic regression will not be applied in the analysis.

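### Protocol 6.4 groups 'unlikely' events with the drug while the analysis sections stop at 'possible', and the 'Treatment-Related TEAEs' summary has no cut-off of its own

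*Protocol*

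**What the plan says.** Protocol 6.4 sets a five-level causality scale in Table 6-2: certain, probable/likely, possible, unlikely, unrelated. It introduces the scale with a grouping rule: "An adverse event is considered associated with the use of the drug if the attribution is certain, probably/likely, possible, or unlikely". Four of the five levels count as drug-associated.

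The analysis text draws the line one level higher. Protocol 7.8.1 says that "adverse events judged by the investigator as at least possibly related to IP, will be summarized" by system organ class and preferred term. SAP 3.2.5 uses the same cut-off: "adverse events judged by the investigator as at least possibly related to IP". On the Table 6-2 scale this means certain, probable/likely and possible.

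The next paragraph of SAP 3.2.5 adds: "Separate summaries will be produced for the following categories, such as TEAEs, SAEs, Treatment-Related TEAEs". Protocol 7.8.1 has the same list. Neither place attaches causality categories to the term *Treatment-Related*.

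The term also appears in Protocol 3.4, where one trigger for stopping study product is "A suspected Grade 3 or higher treatment-related AE" and another is a treatment-related SAE. No cut-off is given there either.

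SAP 3.4, which lists changes from the protocol-planned analyses, does not mention causality.

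**The concern.** Protocol 6.4 is the only section that defines the causality levels and groups them. A programmer looking for the meaning of *Treatment-Related* could go there and count 'unlikely' events. Another could carry down the 'at least possibly' rule from the paragraph above and leave them out. Each could point to current text.

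Safety and tolerability is a secondary objective, and related-event rates tend to be quoted: Protocol 1.2.1 itself summarizes the phase I study by its drug-related TEAEs. At stake is whether a table carrying that label matches the protocol's own grouping, and whether a reader of the study report can tell which rule was used.

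**Working it through.** The plan states no treatment-related AE rate, so there is no figure to reproduce. The check is mainly a comparison of text.

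**Step 1. Set the rules side by side.**

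| Table 6-2 level | Protocol 6.4 grouping | 'At least possibly related' summary (Protocol 7.8.1, SAP 3.2.5) | 'Treatment-Related TEAEs' summary (same sections) |
|---|---|---|---|
| Certain | in | in | in |
| Probable/likely | in | in | in |
| Possible | in | in | in |
| Unlikely | in | out | not stated |
| Unrelated | out | out | out |

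The rules differ in one row. The third column is unambiguous. Only the fourth has an open cell.

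**Step 2. Is 'unlikely' a level that will be used?** Table 6-2 assigns it when the timing makes a relationship improbable and disease or other drugs give a plausible explanation. All subjects have viral pneumonia, receive standard of care, and must have at least two listed risk factors (Protocol 3.2.2), so the level could well be used. Working the other way, Protocol 6.1 excludes non-serious events of expected COVID-19 or influenza progression from AEs. Under *unrelated*, the entry for events before dosing cannot apply to a TEAE, because TEAEs start at first dose (Protocol 6.5.1). Under 6.4 a TEAE therefore escapes only if it is due wholly to factors other than study treatment.

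**Step 3. When do the two readings give different rates?** Let
- *n* = subjects in the arm;
- *a* = subjects with at least one event rated possible or stronger;
- *u* = subjects with no such event but at least one rated unlikely.

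Rate at the 7.8.1/SAP cut-off = *a*/*n*. Rate under the 6.4 grouping = (*a* + *u*)/*n*. Difference = *u*/*n*, whatever *a* is. If *u* = 0 the rates are equal.

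**Step 4. Illustration with assumed counts.** SAP 3.4.1 reports that "only 44 subjects were randomized", and SAP 2.2 gives 1:1 allocation. Assume *n* = 44/2 = 22. The values of *a* and *u* are not in the documents. Taking *a* = 5:

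| *u* | 7.8.1/SAP cut-off | 6.4 grouping | Difference (points) |
|---|---|---|---|
| 0 | 5/22 = 22.7% | 5/22 = 22.7% | 0 |
| 1 | 22.7% | 6/22 = 27.3% | 1/22 = 4.5 |
| 3 | 22.7% | 8/22 = 36.4% | 3/22 = 13.6 |
| 5 | 22.7% | 10/22 = 45.5% | 5/22 = 22.7 |

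The table shows how sensitive a small arm is. It does not estimate what happened. SAP 3.2.2 also calls for summaries by domain, where denominators are smaller and each subject weighs more.

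**The case against.** The strongest reply is that the two analysis sections agree with each other. Protocol 6.4 sits in the AE assessment chapter, speaks of association with the drug, and prescribes no table or rate. The Treatment-Related TEAEs summary comes directly after the 'at least possibly' rule, so the natural reading is that it labels the same set. The mock-up tables and listing specifications are separate documents (SAP 3.6) and may state the cut-off. Little information is at risk in any case: all reported AEs are summarized whatever their causality, and individual data are listed (SAP 3.3.11).

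Much of this stands. A reader might infer that the plan gives the related-AE rate two values throughout, or that the protocol's analysis section and the SAP conflict. The documents do not support either. The 'at least possibly' summary has one meaning, and 'unlikely' events stay visible in the all-AE tables. A reader might also take an illustrative gap such as 22.7% against 36.4% as a measured effect. It is not, since the counts are assumed and the exact split by arm is not given.

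The natural reading is still not written down. The difference between *associated* and *related* does not settle it, because Table 6-2 is presented as a scale of causality and the documents give *treatment-related* no separate meaning. A cut-off in the mock-ups would settle the table but leave the wording of Protocol 6.4 in conflict with it.

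**Conclusion.** The point holds in a limited form. Current text contains two groupings of the causality scale, and nothing reconciles them. One planned summary, Treatment-Related TEAEs, is open to both. Its value changes only if at least one subject's sole qualifying event is rated 'unlikely'. The size cannot be known from the documents. At an assumed 22 per arm it is 4.5 percentage points per such subject, and zero if there are none.

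This is a reporting ambiguity in a descriptive safety outcome. It does not touch the efficacy analysis. It is worth correcting because the correction is cheap and the label is one that readers will quote.

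Protocol 3.4 does not enter the rate. It uses the same undefined term, so that passage and 6.4 must be reconciled. This review takes no position on what the stopping rule should be.

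**What to change.** The last subject left on 22 April 2025 (SAP 2.5), so the practical place for the change is the SAP and the study report, before unblinding if that is still possible.

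1. In SAP 3.2.5, state that Treatment-Related TEAEs counts the same categories as the 'at least possibly related' summary: certain, probable/likely and possible.
2. In SAP 3.4, record that this departs from the Protocol 6.4 grouping, which also includes 'unlikely'.
3. In the related-TEAE tables, add a separate count of subjects whose strongest attribution is 'unlikely', so that the 6.4 figure can be recovered by addition.
4. In the study report, note that Protocol 3.4 uses *treatment-related* without a cut-off and that the passage and 6.4 need reconciling.

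The cost is a few sentences and one extra column. Table 6-2 already provides for rating causality on five levels, so no new data are needed.

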6.5. Reporting Procedure

6.5.1. Adverse Event (AE)

Any AE occurring from the time the subject takes the first dose of the IP will be collected as treatment-emergent adverse events (TEAE) and the safety analysis will be carried out with TEAE. All TEAEs, regardless of seriousness, severity, or presumed relationship to study regimen, will be evaluated and recorded by investigators preferably with a diagnosis or medical terminology instead of signs, symptoms, and/or other clinical information on the TEAE form of CRF until recoverable or stable without a further follow-up by investigators' opinions. All measures required for adverse event management must be recorded in the source document and reported according to sponsor instructions.

6.5.2. Serious Adverse Event (SAE)

As any SAE occurs, the investigator must inform sponsor or its delegate within 24 hours of their knowledge of the event by email, fax or telephone.

It is the responsibility of Investigators to review all documents (e.g., site progress notes, laboratory, and diagnostics reports) relative to the AEs/SAEs/SUSARs and record on the appropriate documents. Investigator will transmit the related copies of patient's medical records for SUSAR cases to sponsor. In this instance, all patient identifiers will be blinded on the copies of the medical records prior to submission to the sponsor ASAP. The sponsor should file the initial report of SUSAR to FDA/TFDA within 15 days (7 days for death or life-threatening events) after aware of the event. Completed follow-up report for death or life-threatening events must be filed within 15 days and/or till recoverable or stable without a further follow-up by investigators' opinions.

The SAE and SUSAR shall be reported promptly according to the reporting procedure of each IRB(s).

6.5.3. Pregnancy reporting

Any subject and subject's female partner who becomes pregnant during the study period should be recorded and the information regarding this pregnancy should be collected. When a subject suspects a pregnancy during the study period, a pregnancy test should be conducted. Once pregnancy is confirmed, the subject should be withdrawn from the study (**Section 3.5**). The pregnancy should be reported to the sponsor using the pregnancy report form. The Obstetrician/Gynecologist of the female subject or male subject's partner should be notified the study information. Because information of specific tests regarding this IP is not clear yet, whenever possible, a pregnancy should be followed to term or to any premature terminations reported. Additionally, the status of the mother and child should

be reported to the sponsor after delivery. Although pregnancy occurring during the study is not considered as an adverse event, abnormal pregnancy outcomes (e.g., spontaneous abortion, fetal death, stillbirth, congenital anomalies, and ectopic pregnancy) are considered SAEs.

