3.5. Discontinuation/Withdrawal from the Study

Subjects will be followed and monitored over the course of the study stated in **Section 5.1** Visit Schedule. If a subject does not attend any of the regularly scheduled visits, the subject will not be deemed as withdrawn, but the missed visit(s) will be considered as missing data in the study registry. Subjects may be discontinued from study product CX-4945 (**Section 3.4**) at the discretion of the Investigator if any severe, untoward effects occur to the subjects during the treatment phase. However, subjects may not be terminated from the study because of AEs.

If a subject, whether continuing study product CX-4945 or not, fails to return to any scheduled visits (i.e., lost to follow-up), or if the Investigator determines that it is in subject's best interest to be prematurely withdrawn from the study, the Investigator must determine the primary reason for subject's premature withdrawal and document this incidence in the eCRF, including the date of occurrence and the reason(s). All study-related information collected prior to subject's withdrawal will be retained and maintained in the study analysis unless otherwise explicitly requested by the subject; however, no further efforts will be made to obtain or record additional medical information about the subject. Subjects will be withdrawn from the study prematurely due to any of the following circumstances:

- Subject (or legal representative) decides to withdraw consent at any time.
- Subject, determined by the Investigator (or designee), is no longer physically or mentally feasible for further participation in the study.
- Subject is lost to follow-up.

- The sponsor terminates the study.

All collected/generated data and information about the subjects in the study prior to the time of study discontinuation will be recorded and analyzed, including the date and reason(s) to discontinue the study.

All subjects who have received at least one dose of study medication will be encouraged to complete all tests scheduled for the ET wherever possible at the time of the subject's withdrawal within 7 days.

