5.1.2. Visit 2 (Day 1) – Baseline, randomization, the first day of treatment

The following procedures should be evaluated at the visit:

- (1) Collect any change of medical history. Any pre-treatment medical events will be recorded as medical history
- (2) Conduct physical exam

- (3) Measure vital signs
- (4) Collect NIAID 8-point ordinal scale
- (5) Assess pulse oxygen saturation: measure SpO₂ and record FiO₂
- (6) Collect urine and blood samples for the following laboratory tests.
 - Hematology
 - Blood Chemistry
 - Coagulation
 - Urinalysis
 - Biomarker evaluations
- (7) Collect nasopharyngeal swab samples for RT-PCR
- (8) Randomization
- (9) Dispense study drug. The study drugs will be administered for 5 consecutive days starting on Day 1 and completing on Day 5, or on Day 6 if only one dose is administered on Day 1.
- (10) Provide SOC/supportive care (as needed)
- (11) Record any change of concomitant medication
- (12) Instruct the use of the Electronic Patient Reported Outcomes (ePRO) for dose administrations and body temperature record
- (13) Record hospitalization events and ER visit, if any
- (14) Check mortality status
- (15) Record adverse events after drug administration, if any

5.1.3. Visit 3 (Day 7 ± 1 Day) – The end of treatment (EOT)

The following assessments should be evaluated at this visit:

- (1) Conduct physical exam
- (2) Measure vital signs
- (3) Collect NIAID 8-point ordinal scale
- (4) Assess pulse oxygen saturation: measure SpO₂ and record FiO₂
- (5) Perform 12-lead ECG
- (6) Perform chest X-ray
- (7) Collect urine and blood samples for the following laboratory tests.
 - Hematology
 - Blood Chemistry
 - Coagulation

- Urinalysis
- Biomarker evaluations

(8) Perform pregnancy test: Only for female with child bearing potential

(9) Collect nasopharyngeal swab samples for RT-PCR

(10) Check ePRO completion status

(11) Provide SOC/supportive care (as needed)

(12) Check drug accountability and compliance. Return all unused study drugs and empty containers

(13) Record hospitalization events and ER visit, if any

(14) Record any change of concomitant medication

(15) Record adverse events and check mortality status, if needed

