5.1.4. Visit 4 (Day 15 ± 2 Days) – 1st Follow-up

The following assessments should be evaluated at this visit:

- (1) Conduct physical exam
- (2) Measure vital signs
- (3) Collect NIAID 8-point ordinal scale
- (4) Assess pulse oxygen saturation: measure SpO₂ and record FiO₂
- (5) Perform 12-lead ECG
- (6) Perform chest X-ray
- (7) Collect urine and blood samples for the following laboratory tests.
 - Hematology
 - Blood Chemistry
 - Coagulation
 - Urinalysis
 - Biomarker evaluations
- (8) Provide SOC/supportive care (as needed)
- (9) Check ePRO completion status
- (10) Record hospitalization events and ER visit, if any
- (11) Record any change of concomitant medication
- (12) Record adverse events and check mortality status, if needed

5.1.5. Visit 5 (Day 29 ± 3 Days) – 2nd Follow-up, the end of study (EOS)/early termination (ET)

The following assessments should be evaluated at this visit:

- (1) Conduct physical exam
- (2) Measure vital signs
- (3) Collect NIAID 8-point ordinal scale
- (4) Assess pulse oxygen saturation: measure SpO₂ and record FiO₂
- (5) Perform 12-lead ECG
- (6) Perform chest X-ray
- (7) Collect urine and blood samples for the following laboratory tests.
 - Hematology
 - Blood Chemistry
 - Coagulation
 - Urinalysis
 - Biomarker evaluations
- (8) Perform pregnancy test: Only for female with child bearing potential when early termination occurs before the completion of Visit 3
- (9) Collect nasopharyngeal swab samples for RT-PCR (only performed when early termination occurs before the completion of Visit 3)
- (10) Provide SOC/supportive care (as needed)
- (11) Check ePRO completion status (as needed)
- (12) Record hospitalization events and ER visit, if any
- (13) Record any change of concomitant medication
- (14) Record adverse events and check mortality status, if needed

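### Protocol 3.4 keeps a pregnant subject in the study off product, while 6.5.3 withdraws her, so her event and safety follow-up to Day 29 is not assured

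*Protocol*

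**What the plan says.** Protocol 3.4 gives a list of circumstances in which study product must be stopped, and pregnancy is one of them. The same section states: "Discontinuation of study product CX-4945/placebo does not mean discontinuation from the study, and the remaining study procedures will be completed".

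Protocol 6.5.3 gives a different instruction: "Once pregnancy is confirmed, the subject should be withdrawn from the study", with a cross-reference to Section 3.5. It also asks that the pregnancy be followed to term where possible and treats abnormal outcomes as serious adverse events (SAEs).

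Protocol 3.5 lists four circumstances for withdrawal: consent withdrawn, further participation no longer feasible, loss to follow-up, and termination by the sponsor. Pregnancy is not among them, although the feasibility item or the investigator's best-interest judgment could be stretched to cover it. After withdrawal, "no further efforts will be made to obtain or record additional medical information about the subject". One visit is still offered, within 7 days of withdrawal: "All subjects who have received at least one dose of study medication will be encouraged to complete all tests scheduled for the ET".

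On timing, Protocol 5.1.2 has dosing "starting on Day 1 and completing on Day 5, or on Day 6 if only one dose is administered on Day 1". Protocol 5.2.5.9 schedules pregnancy tests at screening and Day 7. The primary endpoint (Protocol 2.1) covers Day 1 to Day 29, and 5.2.4.1 follows hospitalization to Day 29. The SAP does not address pregnancy.

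**The concern.** A site that confirms a pregnancy while the subject is still dosing has two instructions: stop product and carry on with the schedule, or withdraw her. Both cannot be carried out in full, because 3.4 requires the remaining procedures and 3.5 stops new data collection.

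At stake is the rest of the Day 1 to Day 29 observation period in a subject exposed to the drug around the time of a pregnancy. New hospitalizations, emergency room visits and adverse events would no longer be collected on schedule. Protocol 6.5.3 itself says that information on this product in pregnancy is not yet clear, so this is a subject whose safety data one would want.

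There is also a small analysis consequence. Under SAP 3.2.3 and 3.3.2, a subject who leaves before Day 29 without an event is labelled 'Treatment Fail'. Under SAP 3.2.11 that label enters the sensitivity analyses of the primary and all-cause endpoints.

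A second inconsistency sits beside the first: 6.5.3 wants the pregnancy followed to term, but the 3.5 sentence that ends data collection makes no exception for it.

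**Working it through.** **Step 1. The rules side by side.**

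| | Protocol 3.4 | Protocol 6.5.3 with 3.5 |
|---|---|---|
| Study product | stopped | not mentioned; withdrawal would end it |
| Study participation | continues | ends |
| Data after that point | remaining scheduled procedures | ET visit encouraged within 7 days, then no further collection |
| Pregnancy outcome | not mentioned | followed to term where possible |

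**Step 2. When they conflict.** Dosing ends on Day 5, or on Day 6 if only one dose was taken on Day 1. Up to then the product-stop rule has something to act on, and the two sections disagree about what follows. From Day 7 there is no product left to stop, so 6.5.3 alone decides. The Day 7 test (Visit 3, window Day 6 to 8) therefore usually falls after the conflict has passed. During dosing, confirmation needs a test done on suspicion (6.5.3) or a Visit 3 held on Day 6.

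**Step 3. Days of scheduled capture at risk if 6.5.3 is followed.** The plan gives no figure here to reproduce. Let d be the day on which pregnancy is confirmed, and assume withdrawal on the same day. The end of the window is nominal Day 29 (Protocol 2.1).

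- Without an ET visit: 29 − d
- With an ET visit at the 7-day limit: max(0, 29 − (d + 7))

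| Confirmation day d | No ET visit | ET visit on d + 7 |
|---|---|---|
| 1 (conflict) | 28 | 21 |
| 6 (last possible dosing day) | 23 | 16 |
| 7 (scheduled test) | 22 | 15 |
| 8 (end of Visit 3 window) | 21 | 14 |
| 22 | 7 | 0 |
| 29 | 0 | 0 |

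For a Day 7 test the result is 29 − 7 = 22 days, or 29 − 14 = 15 days. An earlier ET visit recovers fewer than 7 days, so 15 is the smallest loss and 22 the largest. If 6.5.3 followed 3.4, the scheduled loss would be 0.

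**Step 4. What survives withdrawal.**

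- The ET visit, if she attends, records hospitalization, emergency room visits, adverse events and mortality (Protocol 5.1.5).
- Adverse events already recorded are followed until recovered or stable (6.5.1).
- An SAE must be reported within 24 hours of the investigator learning of it, with no stated exception for withdrawn subjects (6.5.2). Hospitalization and death meet the SAE definition (6.2).
- Pregnancy outcome, and the status of mother and child after delivery, are reported (6.5.3).

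What is not assured is systematic collection of new events from withdrawal, or from the ET visit, to Day 29.

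**Step 5. Analysis.** 'Treatment Fail' is added to the event rate only in the sensitivity analyses (SAP 3.2.3 and 3.2.11).

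**The case against.** The strongest reply is that the sections can be read together. Section 3.4 says only that stopping product does not by itself mean leaving the study; 6.5.3 is the specific rule for pregnancy and adds withdrawal, using the general routes in 3.5. On that reading an investigator stops product and then withdraws her. This is a possible reading, but it leaves 3.4's instruction to complete the remaining procedures without effect for one of the circumstances that 3.4 itself lists. Neither section says that 6.5.3 takes precedence, and 3.5 does not name pregnancy. The mismatch stands.

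Other parts of the reply succeed, and they limit the point:

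- A reader might infer that withdrawal ends all capture of new events. It does not, given SAE reporting on the investigator's knowledge, the ET visit and pregnancy follow-up. Only scheduled collection is lost.
- A reader might take the 22 or 15 days as the size of the conflict. They measure what the withdrawal rule does after dosing, when 3.4 has nothing left to stop.
- A reader might argue that 6.5.3 breaks the 3.5 rule that "subjects may not be terminated from the study because of AEs". It does not: 6.5.3 states that pregnancy is not an adverse event, so that bar does not reach it.
- A reader might take the documents' silence to mean that no pregnancy occurred. They do not say either way.

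**Conclusion.** Protocol 3.4 and 6.5.3 give different instructions for a pregnant subject, and the SAP does not choose between them. The conflict itself is confined to dosing, Day 1 to Day 5 or 6. After that, 6.5.3 applies alone, and scheduled collection of new events to Day 29 is not assured: up to 22 days for a positive Day 7 test, or 15 with an ET visit on Day 14. These counts assume withdrawal on the day of confirmation and a nominal Day 29.

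This is a minor correction for a rare case. Entry requires a negative pregnancy test, contraception, pneumonia severity class II or III and at least two risk factors (Protocol 3.2.2), and 44 subjects were randomized (SAP 3.4.1). The number of women of childbearing potential is not given, so no expected count can be worked out. A reader might infer that a trial result is affected. The documents do not support that: no pregnancy is described, and the 'Treatment Fail' label reaches only sensitivity analyses.

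**What to change.** For the next protocol:

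- Replace the withdrawal sentence in 6.5.3 with: 'Once pregnancy is confirmed, study product should be discontinued (Section 3.4) and the subject remains in event and safety follow-up to Day 29.'
- In 3.5, exempt pregnancy-outcome follow-up from the sentence that ends data collection after withdrawal.

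For this trial, whose last subject left on 22-APR-2025 (SAP 2.5), the study report should state whether any pregnancy occurred and how it was handled. SAP 3.2.8 already summarizes the reasons for all discontinuations, so this adds about one sentence.

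The cost is wording in two protocol sections and no SAP change. Compared with 3.4 as written, no follow-up is added. Compared with 6.5.3 as written, event and adverse event collection to Day 29 is added; for a Day 7 confirmation that means Visits 4 and 5 in place of one encouraged ET visit.
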